4. SUBJECT REGISTRATION

All subjects must be registered through HCRN's electronic data capture (EDC) system. A subject is considered registered when an "On Study" date is entered into the EDC system. Subjects must be registered prior to starting protocol therapy.

5. TREATMENT PLAN

This is a Phase II, open-label, safety, pharmacodynamic and efficacy study of entinostat in combination with nivolumab and ipilimumab in subjects with metastatic RCC who have progressed on ipilimumab + nivolumab regimen or nivolumab alone. Prior to Phase II, a safety lead-in will be conducted to establish the RP2D of entinostat when used in combination with ipilimumab + nivolumab (see Section 5.1). Subjects will initially be treated with the combination of oral entinostat and intravenous (IV) nivolumab plus ipilimumab. Entinostat will be dosed weekly, and nivolumab and ipilimumab will be dosed every 3 weeks, for a total of four, 3-week cycles. Following these first four cycles, entinostat will continue to be administered weekly in combination with nivolumab every 4 weeks or every 2 weeks based on subject tolerance. Ipilimumab will be discontinued. Treatment continued until disease progression or prohibitive toxicity. Anti-tumor activity will be assessed by radiological tumor assessments conducted at baseline and every 6-8 weeks thereafter using RECIST version 1.1.

Due to Funder decision, enrollment will halt after completion of accrual to the safety lead in group. This decision is a result of a shift in priorities at the Funder level and not due to safety issues. Subjects currently on treatment will continue until the criteria for treatment continuation as defined above is met.

5.1 Study Treatment Administration

5.1.1 Cycles 1-4 (cycle =21 days)

Drug	Dose	Route	Schedule ¹	Cycle Length
Entinostat	5mg, 3mg, or 2mg ²	PO	Days 1, 8, 15	21 days
Nivolumab	3 mg/kg	IV over 30 minutes	Day 1	
Ipilimumab	1 mg/kg ³	IV over 30 minutes	Day 1	

¹ A window of \pm 3 days may be applied to all study visits to accommodate observed holidays, inclement weather, scheduling conflicts etc. Date and time of each drug administration should be clearly documented in subject's chart or on drug diary and in the electronic case report forms (eCRFs).

² See Section 5.2 on the Safety Lead-In for determining the RP2D of entinostat

³ Use the subject's actual (not ideal) body weight for dosing as per the American Society of Clinical Oncology (ASCO) guidelines on dosing of obese adult subjects. If a subject's weight changes by more than 10% from Cycle 1 Day 1 the dose of nivolumab and ipilimumab should be recalculated.

5.1.2 Cycles 5+ (cycle = 28 days)

Drug	Route	Dose	Schedule ¹	Cycle Length	
Entinostat	PO	RP2D ²	Days 1, 8, 15 and 22	28 days	
Nivolumab ³	IV over 30 minutes	480 mg	Day 1		
		Subjects that do not tolerate every 4 week dosing			
		240 mg	Day 1 and 15		

¹ A window of \pm 3 days may be applied to all study visits to accommodate observed holidays, inclement weather, scheduling conflicts etc. Date and time of each drug administration should be clearly documented in subject's chart or on drug diary and in the eCRFs.

² See Section 5.2 on the Safety Lead-In for determining the RP2D of entinostat

³ See Section 5.4.2 for additional details regarding nivolumab administration during the maintenance period. Subjects will receive 480 mg on Day 1 of each cycle. Subjects that do not tolerate an every 4 week dosing regimen may receive nivolumab 240 mg on Day 1 and Day 15 of each cycle.

5.2 Safety Lead-In

Entinostat in combination with fixed dose nivolumab and ipilimumab will be tested using a 3+3 dose de-escalation design (5 mg, 3 mg and 2 mg). The starting dose level of entinostat will be 5 mg PO every 7 days, which is 50% of the recommended entinostat dose when used as single agent. Dose limiting toxicities (DLTs) will be evaluated during the first two cycles (6 weeks) of treatment. Each dose level will have up to 6 patients treated.

The trial will proceed in a 3+3 fashion. The study will recruit the first 3 patients starting at the highest dose level (5 mg). If there is 0 or 1 DLT, then the study will recruit additional 3 patients treated at that dose level. If \leq 1 DLT is observed after 6 patients at this dose, that will be the

RP2D. If any time at this dose level, more than 1 DLT is observed, then the accrual to this dose level will be stopped, and the study will be de-escalated to the next dose level (3mg).

This procedure is repeated at the second dose level cohort (3 mg). At this dose level, the study will study 3 patients first. If there is 0 or 1 DLT, then the study will recruit additional 3 patients treated at that dose level. If ≤ 1 DLT is observed after 6 patients at this dose, that will be the RP2D. If any time at this dose level, more than 1 DLT is observed, then the accrual to this dose level will be stopped, and the study will be de-escalated to the next dose level (2 mg).

Up to 6 patients will be enrolled and treated at the last dose level cohort (2 mg). At this dose level, the study will study 3 patients first. If there is 0 or 1 DLT, then the study will recruit additional 3 patients treated at that dose level. If ≤ 1 DLT is observed after 6 patients at this dose, that will be the RP2D. If any time at this dose level, more than 1 DLT is observed, then the accrual to this dose level will be stopped, and the study will be terminated and no RP2D can be reached.

For the Safety Lead-in, up to 18 patients could be enrolled. The RP2D will be the highest of these 3 dose levels of entinostat that results in ≤ 1 out of 6 subjects experience a DLT. The 6 subjects in the RP2D cohort will be included in Stage 1 of the Simon's optimal two-stage Phase II study.

5.2.1 Dose Limiting Toxicity (DLT)

DLTs are defined as:

- Prolonged (>1 week) Grade ≥ 3 anemia attributable to entinostat and/or nivolumab plus ipilimumab during the first 2 cycles (6 weeks) of the combination treatment.
- Grade 3-4 febrile neutropenia
- Grade 4 thrombocytopenia
 - Grade 3 thrombocytopenia with hemorrhage
- Grade 3-4 nonhematological toxicities attributable to entinostat and/or nivolumab plus ipilimumab during the first 2 cycles (6 weeks) of the combination treatment. Exceptions include:
 - Grade 3 fatigue < 7 days
 - Grade 3 nausea lasting < 72 hrs in patients who have not received adequate anti-emetic therapy
 - Grade 3-4 vomiting lasting < 72 hrs in patients who have not received adequate anti-emetic therapy
 - Grade 3-4 diarrhea lasting < 72 hrs in patients who have not received adequate anti-diarrheal therapy
 - Asymptomatic laboratory abnormalities lasting < 72 hrs
 - Asymptomatic elevations in AST or ALT lasting < 7 days.
- AST or ALT $> 3 \times$ ULN in patients in whom these abnormalities cannot be attributed to another, non-drug related cause
- Total bilirubin $> 2 \times$ ULN in patients whom this abnormality cannot be attributed to another, non-drug related cause

5.3 Phase II

Due to Funder decision, enrollment will halt after completion of accrual to the safety lead in group and not proceed to Phase II. This decision is a result of a shift in priorities at the Funder level and not due to safety issues. Subjects currently on treatment will continue until the criteria for treatment continuation as defined above is met.

The six subjects treated at the RP2D of entinostat from the Safety Lead-in would have been rolled over into Stage 1 of the Phase II portion of the study, and an additional 15 subjects would have been enrolled. If at most one response is seen within Stage 1, then the trial would have been terminated for futility. Otherwise, accrual would have continued to a total of 41 subjects treated at the RP2D. Pre-medication Subjects do not require routine pre-medication prior to each treatment. However, local institutional standards may be followed, at the discretion of the investigator.

See Section 5.6.1 for recommended premedication in subjects who experience infusion related reaction (IRR), allergic reaction or bronchospasm associated with nivolumab and/or ipilimumab.

5.4 Study Drug(s) Administration

5.4.1 Entinostat

Entinostat (5mg, 3mg, or 2 mg) will be administered orally every 7 days. Treatment will continue until disease progression in the absence of prohibitive toxicities.

Entinostat is to be taken on an empty stomach, at least 2 hours after a meal and at least 1 hour before the next meal. Entinostat tablets should not be split, crushed, or chewed. If entinostat is vomited, dosing should not be re-administered but instead the dose should be skipped. Subjects should record the emesis and the skipped dose in their drug diary. If an entinostat dose is missed, it may be taken up to 48 hours after the scheduled dosing time. If it is not taken within the 48 hour window, the dose should not be taken and should be counted as a missed dose. The subject should take the next scheduled dose per protocol and record the missed dose in their drug diary.

5.4.1.1 Entinostat Compliance

Subjects will complete a diary to document their drug compliance. They will be instructed to return all unused drugs (partially used and empty containers) and their diary at each clinic visit. Site staff will perform accountability of the returned drug, assess subject compliance, and educate the subject on the directions for self-medication.

5.4.2 Nivolumab

Nivolumab 3mg/kg will be administered as a 30 minute IV infusion on Day 1 of each 21 day cycle for 4 cycles. During maintenance, nivolumab will be administered at 480 mg IV on Day 1 of each 28 day cycle. Subjects that do not tolerate an every 4 week dosing regimen may receive nivolumab 240 mg IV on Day 1 and Day 15 of each 28 day cycle. The decision to change the dosing regimen is at the site investigator's discretion. If a subject transitions to an every 2 week dosing regimen that subject will remain on that dosing regimen for the remainder of their treatment. See Section 5.6.1 for management of any infusion reaction that occurs with nivolumab. Sites should make every effort to target infusion timing as close to 30 minutes as

possible. However, given the variability of infusion pumps from site to site, a window of \pm 10/-5 minutes is acceptable. Treatment will continue in the absence of prohibitive toxicities or disease progression.

5.4.3 Ipilimumab

Ipilimumab 1mg/kg will be administered as a 30 minute IV infusion on Day 1 of each 21 day cycle for 4 cycles. See Section 5.6.1 for management of any infusion reaction that occurs with ipilimumab.

Sites should make every effort to target infusion timing as close to 30 minutes as possible. However, given the variability of infusion pumps from site to site, a window of \pm 10/-5 minutes is acceptable. Treatment will continue for up to 4 cycles, in the absence of prohibitive toxicities or disease progression.

Nivolumab will be given first, followed by 30 minutes of monitoring, and then ipilimumab given second, followed by 30 minutes of monitoring. If the subject does not have an infusion reaction during the first cycle, the post-ipilimumab monitoring may be discontinued for subsequent cycles at the discretion of the treating physician. However, monitoring between the nivolumab/ ipilimumab infusions will continue throughout all 4 cycles.

5.5 Concomitant Medications

All concomitant medications received within 28 days before the first dose of trial treatment and 30 days after the last dose of trial treatment should be recorded. Subjects who are still being followed for a serious adverse events (SAE) will have SAE-specific concomitant medications recorded until resolution of the SAE.

5.5.1 Allowed Concomitant Medications

All treatments that the site investigator considers necessary for a subject's welfare may be administered at the discretion of the site investigator in keeping with the community standards of medical care. All concomitant medications will be recorded on the eCRF including all prescription, over-the-counter (OTC), herbal supplements, and IV medications and fluids. If changes occur during the trial period, documentation of drug dosage, frequency, route, and date may also be included on the eCRF. Use of bisphosphonates during study treatment is at site investigator's discretion.

5.5.2 Prohibited Concomitant Medications

Medications or vaccinations specifically prohibited in the exclusion criteria are not allowed during the ongoing trial. If there is a clinical indication for one of these or other medications or vaccinations specifically prohibited during the trial, discontinuation from trial therapy or vaccination may be required. The site investigator should discuss any questions regarding this with the sponsor-investigator via the HCRN project manager. The final decision on any supportive therapy or vaccination rests with the site investigator and/or the subject's primary physician. There are no prohibited therapies during the Post-Treatment Follow-up Phase.

The following medications are excluded while the subject is receiving study drugs:

- Any other HDAC inhibitor, including valproic acid
- DNA methyltransferase inhibitors

- Any additional anticancer agents, such as chemotherapy, immunotherapy, targeted therapy, biological response modifiers, or endocrine therapy, will not be allowed, even if utilized as treatment of non-cancer indications.
- Any therapeutic investigational agents
- Radiation therapy
Note: Radiation therapy to a symptomatic solitary lesion or to the brain may be considered on an exceptional case-by-case basis after consultation with Sponsor Investigator. The subject must have clear measurable disease outside the radiated field. Administration of palliative radiation therapy will be considered clinical progression.
- Traditional herbal medicines; these therapies are not fully studied and their use may result in unanticipated drug-drug interactions that may cause or confound the assessment of toxicity
- Live vaccines within 30 days prior to the first dose of trial treatment and while participating in the trial. Examples of live vaccines include, but are not limited to, the following: measles, mumps, rubella, varicella/zoster, chicken pox, yellow fever, rabies, BCG, and typhoid (oral) vaccine. Seasonal influenza vaccines for injection are generally killed virus vaccines and are allowed; however intranasal influenza vaccines (e.g. Flu-Mist®) are live attenuated vaccines, and are not allowed.
- Systemic glucocorticoids (>10 mg prednisone equivalent) for any purpose other than to modulate symptoms from an event of clinical interest of suspected immunologic etiology. Brief, limited use of systemic corticosteroids (≤ 7 days) are permitted where such use is considered standard of care (e.g. as premedication for contrast allergy or for COPD exacerbation). Inhaled or topical steroids, and adrenal replacement doses of steroids (for example prednisone 10mg daily) are permitted while on study.

5.5.3 Recommendations for Medications to be Avoided

- Sensitive substrates of CYP1A2, CYP2C8, CYP3A with a narrow therapeutic window (see Appendix 1)
- Drugs that are known to inhibit or induce P-gp (see Appendix 1)

5.6 Supportive Care

Subjects should receive appropriate supportive care measures as deemed necessary by the site investigator.

Suggested supportive care measures for the management of adverse events (AEs) with potential immunologic etiology are outlined below. Where appropriate, these guidelines include the use of oral or intravenous treatment with corticosteroids as well as additional anti-inflammatory agents if symptoms do not improve with administration of corticosteroids. Note that several courses of steroid tapering may be necessary as symptoms may worsen when the steroid dose is decreased. For each disorder, attempts should be made to rule out other causes such as metastatic disease or bacterial or viral infection, which might require additional supportive care. The treatment guidelines are intended to be applied when the investigator determines the events to be related to nivolumab or ipilimumab.

5.6.1 Suggested supportive care measures for the management of AEs that are related to nivolumab or ipilimumab

Immuno-oncology (I-O) agents are associated with AEs that can differ in severity and duration than AEs caused by other therapeutic classes. Nivolumab and ipilimumab are considered immuno-oncology agents in this protocol. Early recognition and management of AEs associated with immuno-oncology agents may mitigate severe toxicity. Management algorithms have been developed to assist investigators in assessing and managing the following groups of AEs: Gastrointestinal, Renal, Pulmonary, Hepatic, Endocrinopathies, Skin, Neurological.

For subjects expected to require more than 4 weeks of corticosteroids or other immunosuppressants to manage an AE, consider recommendations provided in the algorithms. These algorithms are found in Appendix 2. The guidance provided in these algorithms should not replace the site Investigator's medical judgment but should complement it.

Subjects on IV steroids may be switched to an equivalent dose of oral corticosteroids (e.g. prednisone) at start of tapering or earlier, once sustained clinical improvement is observed. Lower bioavailability of oral corticosteroids should be taken into account when switching to the equivalent dose of oral corticosteroids.

Subjects who are started on steroids for management of an immune-related event should not resume immunotherapy until steroids have been tapered to \leq prednisone 10mg daily or an equivalent dose of an alternative corticosteroid.

Management of Infusion Reactions: Acute infusion reactions (which can include cytokine release syndrome, angioedema, or anaphylaxis) are different from allergic/hypersensitive reactions, although some of the manifestations are common to both AEs. The table below shows treatment guidelines for subjects who experience an infusion reaction associated with administration of nivolumab or ipilimumab.

Management of Infusion Related Reaction (IRR), Allergic Reaction, Hypersensitivity reaction or Bronchospasm from Nivolumab or Ipilimumab

Description	Action
CTCAE Grade 1 IRR, allergic reaction or bronchospasm	Remain at bedside and monitor subject until recovery from symptoms. For subsequent infusions, it is recommended that diphenhydramine 50 mg (or equivalent) and/or paracetamol (acetaminophen) 325 to 1000 mg should be administered at least 30 minutes prior to subsequent infusions of nivolumab or ipilimumab. If necessary, corticosteroids (recommended dose: up to 25 mg of IV hydrocortisone or equivalent) may be used.
CTCAE Grade 2 IRR, allergic reaction or bronchospasm	Stop the infusion, begin an IV infusion of normal saline, and treat the subject with diphenhydramine 50 mg IV (or equivalent) and/or paracetamol 325 to 1000 mg (acetaminophen); remain at bedside and monitor subject until resolution of symptoms. Corticosteroid or bronchodilator therapy may also be administered as appropriate. If the infusion is interrupted, then restart the infusion at 50% of the original infusion rate when symptoms resolve; if no further complications ensue after 30 minutes, the rate may be increased to 100% of the original infusion rate. Monitor subject closely. If symptoms recur, then no further

	nivolumab will be administered at that visit. Administer diphenhydramine 50 mg IV, and remain at bedside and monitor the subject until resolution of symptoms. The amount of study drug infused must be recorded on the eCRF. For subsequent infusions, it is recommended that diphenhydramine 50 mg (or equivalent) and/or paracetamol (acetaminophen) 325 to 1000 mg should be administered at least 30 minutes prior to subsequent infusions of nivolumab or ipilimumab. If necessary, corticosteroids (recommended dose: up to 25 mg of IV hydrocortisone or equivalent) may be used.
CTCAE Grade 3 or 4 IRR, allergic reaction, bronchospasm or hypersensitivity reaction¹	Immediately discontinue infusion of nivolumab. Begin an IV infusion of normal saline, and treat the subject as follows. Recommend bronchodilators, epinephrine 0.2 to 1 mg of a 1:1,000 solution for subcutaneous administration or 0.1 to 0.25 mg of a 1:10,000 solution injected slowly for IV administration, and/or diphenhydramine 50 mg IV with methylprednisolone 100 mg IV (or equivalent), as needed. Subject should be monitored until the investigator is comfortable that the symptoms will not recur. Nivolumab or ipilimumab will be permanently discontinued. Investigators should follow their institutional guidelines for the treatment of anaphylaxis. Remain at bedside and monitor subject until recovery from symptoms. In the case of late-occurring hypersensitivity symptoms (eg, appearance of a localized or generalized pruritis within 1 week after treatment), symptomatic treatment may be given (eg, oral antihistamine, or corticosteroids).

¹Hypersensitivity reactions included in CTCAEv4 include anaphylaxis, Stevens-Johnson syndrome and toxic epidermal necrolysis; in the case of late-occurring hypersensitivity symptoms (e.g., appearance of a localized or generalized pruritis within 1 week after treatment), symptomatic treatment may be given (e.g., oral antihistamine, or corticosteroids).

5.7 Contraception

Women of childbearing potential are defined as any female who has experienced menarche and who has not undergone surgical sterilization (hysterectomy or bilateral oophorectomy) or who is not postmenopausal. Menopause is defined clinically as 12 months of amenorrhea in a woman over 45 in the absence of other biological or physiological causes. In addition, women under the age of 62 must have a documented serum follicle stimulating hormone (FSH) level less than 40 mIU/mL. Women of childbearing potential must be willing to abstain from heterosexual intercourse or to use an effective method of contraception from the time of informed consent until 5 months after the last dose of study drug. This timeframe is applicable to breast-feeding as well.

Men who are sexually active with WOCBP must use any contraceptive method with a failure rate of less than 1% per year (i.e., a highly effective contraceptive method). Men receiving study drug and who are sexually active with WOCBP will be instructed to adhere to contraception for a period of 3 months after the last dose of entinostat. This timeframe is applicable to sperm donation.

Subjects should be informed that taking the study medication may involve unknown risks to the fetus (unborn baby) if pregnancy were to occur during the study. In order to participate in the study they must adhere to the contraception requirements for the duration of the study and during

the follow-up period. If there is any question that a subject will not reliably comply with the requirements for contraception, that subject should not be entered into the study.

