¹ Creatinine clearance should be calculated per institutional standard	
Hepatic	
Bilirubin	$\leq 1.5 \times$ ULN OR Direct bilirubin \leq ULN for subjects with total bilirubin levels $> 1.5 \times$ ULN
Aspartate aminotransferase (AST)	$\leq 3 \times$ ULN
Alanine aminotransferase (ALT)	$\leq 3 \times$ ULN
Coagulation	
International Normalized Ratio (INR) or Prothrombin Time (PT) Activated Partial Thromboplastin Time (aPTT)	$\leq 1.5 \times$ ULN unless subject is receiving anticoagulant therapy as long as PT/INR/PTT is within therapeutic range of intended use of anticoagulants

11. Women of childbearing potential (WOCBP) must have a negative serum pregnancy test during screening and a negative urine pregnancy test within 3 days prior to first dose of study drug. If the screening serum test is done within 3 days prior to receiving the first dose of study drug, a urine test is not required.

12. Women of childbearing potential must be willing to abstain from heterosexual intercourse or to use an effective method of contraception from the time of informed consent until 5 months after the last dose of study drug.

13. Men who are sexually active with WOCBP must use any contraceptive method with a failure rate of less than 1% per year. Men receiving study drugs and who are sexually active with WOCBP will be instructed to adhere to contraception for a period of 3 months after the last dose of entinostat.

14. As determined by the enrolling physician or protocol designee, ability of the subject to understand and comply with study procedures for the entire length of the study.

15. Life expectancy of at least 6 months per investigator discretion.

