3: Thyroid function to be checked at screening, Cycle 2 Day 1, Cycle 4 Day 1, then every 3rd cycle thereafter starting with Cycle 6. More frequent testing is at the discretion of the site investigator. TSH will be obtained. T4 and T3 including free versus total testing is at the discretion of the site investigator.

4: For women of childbearing potential (WOCBP): serum pregnancy test during screening and a urine pregnancy test within 3 days prior to first dose of study drugs. If the screening serum test was done within 3 days prior to receiving the first dose of study drugs, a urine test is not required.

5: Tumor response assessment will be performed at screening, prior to Cycle 3 Day 1 then prior to Cycle 5 (±7); Tumor imaging to be performed every 8-12 weeks after Cycle 5 based on investigator discretion. Tumor imaging to be done at treatment discontinuation at discretion of investigator. Baseline bone scan will be obtained if there is any suspicion of metastatic bone involvement. If bone scan is positive at baseline, it will be included with subsequent tumor response assessments as noted above at the discretion of the treating physician. MRI of brain should be performed at screening only to evaluate for the presence of brain metastases. Additional imaging of the brain will be at the discretion of the treating physician. Tumor imaging modality used should be consistent throughout trial.

6: Archival tissue from a metastatic lesion or nephrectomy (metastatic lesion preferred) is required if available and will be obtained at screening. If archival tissue is unavailable, patients will be given the option to consent to a biopsy during the screening phase prior to Cycle 1 Day 1 treatment. All subjects with accessible tumor will be given the option to consent to a second optional biopsy on Cycle 2 Day 1. The Cycle 2 Day 1 samples will be collected ~2 hours following the most recent dose of entinostat. To ensure that these samples are obtained at the correct time, patients are urged to take their entinostat dose in the clinic on the day of on-treatment sample collection. The time of the entinostat dose and the time of sample collection must be recorded.

7: Serial blood samples for PBMCs and plasma, serum will be collected prior to treatment Cycle 1 Day 1, Cycle 2 Day 1, Cycle 4 Day 1, and then every 2nd cycle thereafter starting with Cycle 6.

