10.2.7 Adverse Events

Please refer to the ipilimumab Investigator's Brochure for a complete list of adverse events.

Blockade of CTLA-4 by ipilimumab leads to T-cell activation, with the potential for clinical inflammatory AEs primarily involving the skin (dermatitis/pruritus), GI tract (diarrhea/colitis), liver (hepatitis), endocrine glands (eg, hypophysitis and adrenal or thyroid abnormalities), and other less frequent organs (eg, uveitis/episcleritis). The majority of these inflammatory AEs initially manifested during treatment; however, a minority occurred weeks to months after discontinuation of ipilimumab. The majority of the inflammatory AEs is reversible with the guidance issued below and in Appendix 2. In rare cases, these inflammatory AEs may be fatal.

Gastrointestinal Toxicities

The most common site for ipilimumab-induced GI toxicity was the lower GI tract, and the most common presentation was mild to severe diarrhea or colitis with occasional bloody stools. In some cases, diarrhea began as mild and then worsened. Constipation was rarely associated with ipilimumab administration.

Liver Toxicities

Subjects receiving ipilimumab may develop elevations in LFTs in the absence of clinical symptoms. Occasionally, patients may present with symptoms, including right upper quadrant abdominal pain or unexplained vomiting.

Endocrine Toxicities

The most common inflammatory endocrine toxicities occurring in ipilimumab-treated subjects are hypophysitis and hypopituitarism. Secondary cortisol deficiency (hypoadrenalinism), hypothyroidism or thyroiditis, and, less commonly, other endocrinopathies may occur concomitantly with hypophysitis; however, these may also present as the only or as primary endocrinopathy. Most patients with hypopituitarism presented with nonspecific complaints such as fatigue, visual field defects, confusion, or impotence. Some patients have had headache as the predominant presentation. The majority of subjects with hypopituitarism demonstrated enlarged pituitary glands based on brain magnetic resonance imaging (MRI). Low ACTH and cortisol were the most common biochemical abnormality; abnormal (mostly low) thyroid-stimulating hormone (TSH), free thyroxine (fT4), triiodothyronine (T3), testosterone, or prolactin have also been reported in some subjects.

Skin Toxicities

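### The FSH condition for postmenopausal status in Section 5.7 appears to run the wrong way, within a definition of childbearing potential that needs reconciling

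*Combined protocol and SAP*

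**What the plan says.** All references are to the combined protocol and SAP. Section 5.7 builds the definition in three steps.

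- A WOCBP is a woman past menarche "who has not undergone surgical sterilization (hysterectomy or bilateral oophorectomy) or who is not postmenopausal".
- The clinical rule for that last status reads: "Menopause is defined clinically as 12 months of amenorrhea in a woman over 45 in the absence of other biological or physiological causes".
- As a further requirement, "women under the age of 62 must have a documented serum follicle stimulating hormone (FSH) level less than 40 mIU/mL".

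Other sections then rely on WOCBP status. Inclusion criterion 11 in Section 3.1 states: "Women of childbearing potential (WOCBP) must have a negative serum pregnancy test during screening". Criterion 12 states: "Women of childbearing potential must be willing to abstain from heterosexual intercourse or to use an effective method of contraception", from consent until 5 months after the last dose. Footnote 4 of the study calendar in Section 7 asks the same group for a "serum pregnancy test during screening and a urine pregnancy test within 3 days prior to first dose of study drugs". None of these duties applies to a woman who is not WOCBP.

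FSH is mentioned only in Section 5.7. It is not in the eligibility criteria, in the calendar or in the calendar's footnotes.

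**The concern.** The FSH sentence directly follows the definition of menopause and is worded as an addition to it. Its natural function is therefore to confirm menopause in women young enough for amenorrhoea alone to leave doubt. Because FSH rises when ovarian function ends, a low value does not support menopause. A condition that accepts only values below 40 mIU/mL accepts the women whose result fails to confirm the status they are being given.

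What is at stake is protection of the individual subject. A woman wrongly treated as postmenopausal has neither the serum nor the urine pregnancy test and carries no contraception duty, on a regimen whose fetal risks Section 5.7 itself calls unknown. In the other direction, a postmenopausal woman with a high FSH is put through testing and contraception requirements that she may not need.

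**Working it through.** No sample size, power or error rate is involved, so the check is a truth table built from the text.

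**Inputs, all from Section 5.7**

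- Clinical condition C: age over 45, 12 months' amenorrhoea, no other cause.
- FSH condition F: applies under age 62; requires a documented value below 40 mIU/mL.
- WOCBP: past menarche and not exempted by sterilisation or menopause. This is the evident sense of the sentence; the literal sense is tested below.

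**Rule as written:** postmenopausal = C and (age 62 or over, or F).

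The last column mirrors the inequality. It is there only to show which groups depend on its direction and is not a proposed rule.

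| Unsterilised woman | As written | Inequality mirrored |
|---|---|---|
| Over 45, under 62, C met, documented FSH below 40 | not WOCBP | WOCBP |
| Over 45, under 62, C met, documented FSH above 40 | WOCBP | not WOCBP |
| Over 45, under 62, C met, no FSH documented | WOCBP | WOCBP |
| 62 or over, C met | not WOCBP | not WOCBP |
| Still menstruating, or aged 45 or under | WOCBP | WOCBP |

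Only the first two rows depend on the direction, and they exchange places. The first is the unsafe one: it removes the protections in criteria 11 and 12 and in footnote 4. The second adds burden only.

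**Literal reading of the 'or'.** Taken word for word, WOCBP = past menarche and (not sterilised, or not postmenopausal). For any unsterilised woman the first alternative is already true, so she is WOCBP whatever her age or FSH. Rows one and four would both become WOCBP. The exposure in row one disappears, but an unsterilised woman of 70 would also be WOCBP, and the only women exempted would be those both sterilised and postmenopausal. The menopause and FSH sentences would then do almost nothing.

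**Source of the FSH value.** Section 5.7 requires a documented result, yet Section 7 schedules no FSH at any visit. A site can apply the condition only with a value obtained outside the calendar.

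**The case against.** The strongest reply is that the unsafe route is narrow, and this stands. The FSH sentence adds to the clinical definition and does not replace it. Menstruating women, women aged 45 or under and women of 62 or over are untouched. With no FSH scheduled, many women under 62 may have no value on file, and they default to the protected category. Harm needs an unscheduled FSH below 40 in a woman with a year's amenorrhoea and no recognised cause who is nevertheless fertile.

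The literal 'or' can also be offered as a defence, since it would leave every unsterilised woman protected. It shows that the exposure depends on how that sentence is read. But a reading that leaves the menopause definition nearly idle is a second drafting fault, not a safeguard.

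One might instead attach the FSH sentence to the WOCBP definition, where a low value would point the expected way. Its position after the menopause sentence is against this. On that reading a menstruating woman under 62 with no documented FSH would also fall outside WOCBP, which cannot be intended.

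Three stronger inferences are tempting, and the documents do not support them.

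- A reader might infer that the rule is wrong for essentially every amenorrhoeic woman in the age band. A woman with FSH below 40 who meets the clinical definition may still be postmenopausal; her status is unconfirmed, not shown to be false.
- A reader might infer that prior checkpoint therapy makes the fault worse, because Section 10.2.7 says "The most common inflammatory endocrine toxicities occurring in ipilimumab-treated subjects are hypophysitis and hypopituitarism". That section lists several hormone abnormalities but neither FSH nor amenorrhoea. Recognised pituitary disease would come under other causes in Section 5.7, and patients who stopped the prior regimen for toxicity are excluded. The link is conjecture here.
- A reader might put a head count on it. The documents give no sex or age distribution, so none can be derived.

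**Conclusion.** The point holds in a limited form. The direction of the FSH condition appears reversed. In the evident reading of Section 5.7 it exchanges the classification of two groups: unsterilised women over 45 and under 62 with 12 months' amenorrhoea and no recognised cause, split by a documented FSH below or above 40 mIU/mL. Nothing elsewhere in the documents corrects it.

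The conclusion rests on two assumptions: that FSH rises when ovarian function ends, and that the 'or' in the WOCBP sentence is not meant literally. If the second fails, row one's exposure goes, but the passage then contradicts its own menopause definition and still needs repair.

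The number of women affected cannot be stated. The safety lead-in has a ceiling of 18 subjects and accrual stops after it, so the number may be very small and could be zero. Halting accrual does not make the point moot: subjects already on treatment continue, and the contraception duty runs to 5 months after the last dose. This is a fault in safety classification and drafting. It does not touch the DLT rule, the recommended dose, the response-rate analysis, the sample size or the error rates.

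**What to change.** The sponsor's clinical team should review the direction of the FSH condition in Section 5.7. They should reconcile it with the 'or' in the WOCBP definition, with inclusion criteria 11 and 12, and with the Section 7 calendar, which at present offers no source for the value that the text requires. Changing the inequality alone would leave the other two faults in place. The clinical rule itself is for that team to settle, and none is proposed here.

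Once the text is settled, sites should re-check the WOCBP status of any woman still on treatment, or within 5 months of her last dose, who was classed as not WOCBP on the FSH sentence.

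The cost is a short text correction and a few chart checks. No additional patients and no change to any analysis are needed.
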